3.3 Subgroups, interactions and covariates

The following disease groups will be considered for analyses:

- CMT
- CIDP
- Anti-MAG

All efficacy analyses performed on the three disease groups will be descriptive only due to the sample size of each group. Statistical test will be performed on all patients and not by disease group.

No subgroup analysis is planned.

3.4 Baseline data

Baseline data will be defined as the last non missing value available before the first administration of study treatment.

For all data collected both at selection visit (Visit 1) and inclusion visit (Visit 2), the baseline value will be defined as the assessment closest to and before the start of study medication, *i.e.* visit 2. The selection visit (visit 1) will be taken if the value is not available at inclusion visit.

3.5 Interim analyses

No interim statistical analysis is planned.

3.6 Handling of multiple testing

Not applicable.

3.7 Statistical computer software

For statistical analyses performed by ATLANSTAT, SAS® Enterprise Guide software version 7.1 (SAS® for Windows version 9.4) or higher will be used.

4 ANALYSIS SETS

The following populations will be defined:

- Screened Set (SCR)

All patients who signed the informed consent.

- Included Set (IS)

All patients for whom the study drug is dispensed.

- Safety Set (SS)

All patients who received at least one dose of study medication will be included in the Safety Set.

- Full Analysis Set (FAS)

All patients who received at least one dose of study medication and with at least one assessment at baseline and during the study will be included in Full Analysis Set.

- Per Protocol Set (PPS)

All patients of the FAS and without major protocol deviations will be included in Per Protocol Set.

A table displaying all analysis populations will be presented by disease group and overall. A listing will be also provided.

5 PROTOCOL DEVIATIONS

A protocol deviation is defined as any changes in the study design, study conduct and/or procedures that are not in accordance with the protocol and any study materials originally approved by the Independent Ethics Committee (IEC)/Institutional Review Board (IRB).

A major protocol deviation is defined as a deviation which may affect the subject's rights, safety or well-being or the completeness, accuracy and reliability of the study data and so likely to bias significantly the interpretation of the primary efficacy criterion results.

All protocol deviations will be reviewed, in particular but not limited to:

- Deviations in inclusion and exclusion criteria
- Study treatment duration different from 48 weeks (336 days) \pm 15 days (considering interruption periods if applicable)
- Study treatment interruption > 10 consecutive days
- Deviations in study drug intake/compliance (see section 10, compliance < 80% and > 120% on 48 weeks period)
- Non respect of visit schedule (see section 1.2)
- Intake of concomitant prohibited treatments (See protocol section 5.5),
- Missing or incomplete evaluation of the primary efficacy criterion.

All protocol deviations will be reviewed before study database lock and their grade (minor / major) will be classified before the statistical analysis, during the data review meeting.

The number and percentage of patients having at least one protocol deviation (minor and/or major) and at least one major protocol deviation will be described on the Included Set by disease group and overall.

All deviations will be also listed.

6 DESCRIPTIVE STATISTICS

Data will be summarized depending on the nature of variables:

- Continuous variables: number of patients with observed values, arithmetic mean, standard deviation (SD), minimum, Q1, median, Q3 and maximum. Mean, SD, Q1, median and Q3 will be given with an additional decimal than the reported variable itself.
- Categorical data: number and percentage (%) of patients per class. Regarding the percentage calculation, unless otherwise is specified, missing values will not be considered and one decimal will be provided.

Descriptive statistics will be given by disease group (CIDP, anti-MAG and CMT1) and overall if needed.

7 DISPOSITION OF PATIENTS

The number of screened and included patients should be provided by disease group and overall.

The number and percentage of included patients who completed or withdrew prematurely the study will be tabulated by disease group and overall. Study withdrawal reasons will be also given.

The study duration (weeks) will be provided by disease group and overall and calculated as $[(\text{Date of completion/discontinuation of the study} - \text{date of selection visit} + 1) / 7]$.

A listing will be also provided.

8 DEMOGRAPHIC AND OTHER BASELINE CHARACTERISTICS

Descriptive statistics at baseline (see definition in section 3.5) will be produced by disease group and overall on the FAS population.

If more than 10.0% of the FAS population are excluded from the PPS population, the demographic data and history of the disease will be repeated on the PPS population.

- Demographic data: age (years), sex, number of women with childbearing potential at baseline and for the women with childbearing potential, pregnancy test (HCG) at baseline.

Age will be calculated as integer $[(\text{date of selection visit} - \text{date of birth}) / 365.25]$ with day of birth imputed as defined in section 3.2.

A listing will be provided.

- History of the disease: Time since the first appearance of symptoms (years), progression (yes/no), if yes, time since the progression (years)

Time since the first appearance of symptoms will be calculated as $[(\text{date of selection visit} - \text{date of the first appearance of symptoms} + 1) / 365.25]$

Time since progression will be calculated as $[(\text{date of selection visit} - \text{date of progression} + 1) / 365.25]$

In case of incomplete dates for the first appearance of symptoms or for progression, an imputation will be considered (see section 3.2).

A listing will be provided.

- Medical history: The number and percentage of patients with at least one medical history at selection visit V1 will be described by disease group and overall using the MedDRA codes (version 22.0) of System Organ Classes (SOC) and preferred terms (PT).

Descriptive statistics at baseline for clinical examination and biological testing (except aetiology additional panel) will be included in safety analyses (see section 12).

Descriptive statistics at baseline for MRC sum score, INCAT sensory score, posturography parameters (analysis of walking: all parameters in the condition spontaneous speed; analysis of balance: center of pressure on anterior/posterior axis and center of pressure covered area in the four conditions - open/closed eyes and spread feet (60s)/feet together (60s)), ONLS score, timed

10-meter walk test, 6-min walk test, neurophysiological examination and excitability test will be included in efficacy analyses (see section 10).

9 PREVIOUS AND CONCOMITANT TREATMENTS

Previous and concomitant treatment reported names will be coded in Anatomic Therapeutic Chemical (ATC) codes with WHO-DD Type B3 Mars 2019.

Previous treatments will be defined as treatments stopped strictly before the first administration of study drug.

Concomitant treatments will be defined as treatments stopped the day or after the first administration of study drug or ongoing treatments at the end of study.

The number and percentage of patients with at least one previous treatment will be described according to the ATC1 and ATC2 by disease group and overall on Safety Set population.

In the same way, the number and percentage of patients with at least one concomitant treatment will be summarized according to the ATC1 and ATC2, by disease group and overall on Safety Set population.

In case of missing start/end date of treatment, imputation will be considered to define if previous or concomitant treatment (see section 3.2).

A listing of all previous and concomitant treatments will be provided.

10 ANALYSIS OF EFFICACY

10.1 Main criterion

10.1.1 Main criterion – primary analysis

The primary endpoint will be evaluated using the relative change from baseline to week 48 of the following criteria of demyelination:

- Motor nerve conduction velocity (m/s),
- Distal latency (ms),
- F wave latency (ms),
- Length of motor nerve potential (ms).

A maximum of eight nerves will be assessed for those four criteria:

- Right/left median,
- Right/left ulnar,
- Right/left peroneal,
- Right/left tibial.

Relative change from baseline will be considered as clinically significant for the patient when the value at week 48 is at least 10% improved compared to the baseline value at least for two out of these four criteria in at least three nerves out of eight investigated nerves.

Relative change from baseline will be calculated as $[(\text{value at week 48} - \text{value at baseline}) / \text{value at baseline}] * 100$.

An improve is defined as an increase for the motor nerve conduction velocity, and as a decrease for distal latency, F wave latency and length of motor nerve potential.

Missing values at week 48 for the four criteria will be imputed as LOCF method (see section 3.2).

The primary endpoint, for the primary analysis, will be summarized as the number and percentage of patients with a clinical significant relative change (at least 10%) for at least two out of the four criteria in at least three nerves out of the eight investigated by disease group and overall on the FAS population.

For each of those four criteria, number and percentage of patients with at least 10% improved value at week 48 compared to baseline for at least three nerves out of eight will be summarized by disease group and overall on the FAS population, as well as the number and percentage of patients with a clinical significant change.

As sensitivity analysis, if more than 10.0% of the FAS population are excluded from the PPS population, same analysis will be performed on the PPS population.

10.1.2 Main criterion – secondary analysis

As secondary analysis of the primary endpoint, a description of the four criteria of demyelination will be provided at baseline and week 48, as well as the relative change from baseline at week 48 (as defined in section 10.1.1), by disease group and overall on the FAS population, considering all nerves pooled per patient and parameter. A Wilcoxon signed rank test will be performed overall for each parameter to assess if the relative change from baseline is statistically significant at week 48.

In the same as the primary analysis, missing values at week 48 will be imputed as LOCF method (see section 3.2).

A listing of relative changes for each nerve for each patient and for each criterion of demyelination (motor nerve conduction velocity, distal latency, F wave latency, length of motor nerve potential) will be provided as well as the results of primary criterion (success/failed).

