Overall the four limbs will be investigated, including one motor and one sensitive nerve for a total of maximum 8 nerves. The same protocol will be applied at each visit for one patient, aiming to record on the same nerves the studied demyelination criteria.

The investigator will be free to define the most relevant protocol according to patient disease status at baseline. However, the same protocol will be applied in a patient all along the study and the investigator will apply his best efforts to comply with this rule.

5.7.1.1.1 **Polyneuropathy protocol:**

1. Test most involved limb first if mild; if severe do least involved limb first.
2. Test at least 2 limbs, upper and lower, do 3rd limb for symmetry.
3. Lower extremity do sural sensory, peroneal motor with conduction, tibial motor with an F-wave.
4. Upper extremity do a sensory either median or ulnar, also a motor either median or ulnar with conduction and an F-wave.

5.7.1.1.2 **Polyradiculopathy protocol**

1. Sural sensory ankle; stimulate 14 cm proximal to recording electrode.
2. If sural equivocal or technically difficult:
 - a. Opposite sural
 - b. Median sensory (index); stimulate at wrist and elbow.
3. Peroneal motor (EDB); stimulate at knee and ankle with F-response latency.
4. Tibial motor (abductor hallucis brevis); stimulate knee and ankle with F-response latency.
5. Ulnar motor (hypotenar); stimulate at wrist and elbow with F-response latency.
6. If clinically indicated, consider:
 - a. Median (thenar); stimulate at wrist and elbows with F-response latency.
 - b. Musculocutaneous (biceps brachii); stimulate at axilla.
 - c. Facial (orbicularis oculi); stimulate at ankle of jaw.

d. Trigeminal (orbicularis oculi); stimulate supraorbital nerve.

Electrophysiological measures will be performed at W0, W24 and W48 and following parameters will be recorded in the CRF:

- motor nerve conduction velocity,
- distal latency,
- F wave latency,
- length of motor nerve potential

5.7.1.2 *Excitability testing*

Nerve excitability testing is a non-invasive approach in investigating the pathophysiology of peripheral nerve disorders, which determines the electrical properties of the nerve membrane at the site of stimulation

5.7.1.3 *Medical Research Council (MRC) sum score*

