1 INTRODUCTION

The objective of this Statistical Analysis Plan (SAP) is to ensure the maximum credibility of all study findings. This plan will not repeat all the definitions given in the protocol, but will provide further details of the analyses planned therein.

This Statistical Analysis Plan was prepared and signed prior to the database lock after all patients had completed the study.

This SAP has been written in agreement with:

- The Study Protocol version 4.0 dated 10FEB2017
- The Case Report Form (CRF) version 1.0 dated 16MAY2019.

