3.2 Handling of missing data

To calculate age of the patients, if the month and year of the birth are available, the day of birth will be imputed to the 15th of the month of the birth.

The last observation carried forward (LOCF) approach will be used to handle missingness on the primary evaluation criteria at week 48 (Motor nerve conduction velocity, Distal latency, F wave latency and Length of motor nerve potential). Missing data at week 48 will be replaced by the last available post-baseline value.

Other missing or inconsistency data, especially for the secondary criteria, could be reviewed before the database lock, during the data review meeting, and the management of their imputation will be discussed. Following data review meeting, an imputation considering LOCF approach will be performed regarding missing data of secondary criteria at week 48.

Missing or incomplete dates will be managed as below:

To define Treatment Emergent Adverse Events, missing dates of study drug intake or adverse events will be replaced.

- Missing dates of the first study drug intake

In case of completely missing dates of the first study drug intake, it will be considered equal to the day of the inclusion visit + 1 day at the morning.

If the day and the month are missing:

- If the year is the same as the year of the first study drug intake, it will be estimated by the day of the inclusion visit + 1 day at the morning
- If the year is after the year of the inclusion visit, it will be estimated by the 1st January at the morning

If only the day is missing:

- If the month/year are the same as the month/year of the inclusion visit, it will be estimated by the day of the inclusion visit + 1 day at the morning.
- If the month/year are after to the month/year of the inclusion visit, it will be estimated by the first day of the month at the morning.

If only the time of first study drug intake is missing, it will be considered at the morning.

- Missing dates of the last study drug intake

In case of completely missing dates of the last study drug intake, it will be considered as the date of study completion/discontinuation – 1 day at the evening.

If the day and the month are missing:

- If the year is the same as the year of date of study completion/discontinuation, it will be estimated by the study completion/discontinuation date – 1 day at the evening

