13 TABLES, FIGURES AND LISTINGS SHELLS

Shell tables are available in a separate document (See ShellTables_SERENDEM_version1.0_04NOV2019.docx).

List of outputs:

Table 14.1.1 – Disposition of Patients

Table 14.1.2 – Populations for statistical analyses – Screened Set population

Table 14.1.3 – Protocol deviations – Included Set population

Table 14.1.4 – Demographic characteristics – FAS population

Table 14.1.5 – Demographic characteristics – PPS population

Table 14.1.6 – History of the disease – FAS population

Table 14.1.7 – History of the disease – PPS population

Table 14.1.8 – Medical history – FAS population

Table 14.2.1 – Previous treatments – SS population

Table 14.2.2 – Concomitant treatments – SS population

Table 14.3 – Compliance to the study drug – SS population

Table 14.4.1.1 - Primary endpoint – Primary analysis: Number of patients with at least 10% improvement for at least 2 out of the 4 criteria of demyelination, in at least 3 out of 8 nerves – FAS population

Table 14.4.1.2 - Primary endpoint – Sensitivity analysis: Number of patients with at least 10% improvement for at least 2 out of the 4 criteria of demyelination, in at least 3 out of 8 nerves – PPS population

Table 14.4.1.3 – Primary endpoint – Secondary analysis: Motor nerve conduction velocity (m/s) considering all nerves pooled per patient – FAS population

Table 14.4.1.4 – Primary endpoint – Secondary analysis: Distal latency (ms) considering all nerves pooled per patient – FAS population

Table 14.4.1.5 – Primary endpoint – Secondary analysis: F wave latency (ms) considering all nerves pooled per patient – FAS population

Table 14.4.1.6 – Primary endpoint – Secondary analysis: Length of motor nerve potential (ms) considering all nerves pooled per patient – FAS population

Table 14.4.2.1 – Secondary endpoints: ONLS score – FAS population

Table 14.4.2.2 – Secondary endpoints: MRC subscore: Total muscle (/100) – FAS population

Table 14.4.2.3 – Secondary endpoints: MRC Total score (/180) – FAS population

Table 14.4.2.4 – Secondary endpoints: INCAT Sensory Sum (ISS) score – FAS population

Table 14.4.2.5 – Secondary endpoints: Timed 10-meter walk test (s) – FAS population

Table 14.4.2.6 – Secondary endpoints: Distance 6-min walk test (m) – FAS population

Table 14.4.2.7 – Secondary endpoints: Posturography (spontaneous speed condition) - Speed (m/s) – FAS population

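### Does SAP 10.1.2 need to name the statistic that pools up to eight nerves into one value per patient before the Wilcoxon test?

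*SAP*

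**What the plan says.** SAP 10.1.2 sets a secondary analysis of the primary endpoint. Each criterion (motor conduction velocity, distal latency, F wave latency, length of the motor potential) is described at baseline and at week 48, together with its relative change, "considering all nerves pooled per patient and parameter. A Wilcoxon signed rank test will be performed overall for each parameter". Relative change is taken from SAP 10.1.1: week-48 value minus baseline value, divided by the baseline value, times 100. That section allows at most eight nerves per criterion.

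The output list in SAP 13 repeats the phrase for Tables 14.4.1.3 to 14.4.1.6, for example "Secondary analysis: Motor nerve conduction velocity (m/s) considering all nerves pooled per patient", with units of m/s or ms. Neither place names a pooling statistic. The table shells are a separate document that was not available for this review.

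Four other places bear on the reading:

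- SAP 6 summarises by patient: "Continuous variables: number of patients with observed values, arithmetic mean, standard deviation".
- SAP 3.3 takes the whole sample as the basis for testing: "Statistical test will be performed on all patients and not by disease group".
- Protocol 5.7.1.1 aims at matched nerves: "The same protocol will be applied at each visit for one patient, aiming to record on the same nerves the studied demyelination criteria".
- SAP 3.2 fills gaps by LOCF: "Missing data at week 48 will be replaced by the last available post-baseline value".

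**The concern.** Several statistics can be called pooled: the mean or median of the nerve-level relative changes, the relative change of the patient's mean value, a mean log ratio, or all nerves stacked as separate observations. They do not behave alike. A relative change divides by a baseline measured with error, so a plain mean of nerve-level changes is pushed upward even when nothing has changed. Stacking ignores that nerves of one patient belong together.

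These are the only significance tests on the four primary criteria. The study is open label, and the SAP was signed after the last patient had finished. A reader could fear that the pooling was left open until results could be seen, or that a programmer would choose a statistic that rejects too often.

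**Working it through.** The plan states no power, SD or effect size for this test, so there is no figure to reproduce.

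**Inputs from the documents.** 15 patients (SAP 1.3); at most eight nerves (SAP 10.1.1); two-sided 5% (SAP 3.1); one overall test per criterion (SAP 3.3 and 10.1.2).

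**Assumed, because the documents give none.** Measurement CV per visit of 5% to 20%; between-patient SD of the true log change of 0, 0.05 or 0.10; independent error at the two visits; the same nerves at both visits.

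**Step 1: what the text requires.** SAP 10.1.2 wants baseline and week-48 descriptions with nerves pooled per patient, and the table titles carry m/s and ms. A pooled raw value is therefore needed at each visit. Applying the SAP 10.1.1 formula to those two values gives one relative change per patient. A mean log ratio does not meet that formula. A mean of nerve-level changes does not supply the two pooled raw values.

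**Step 2: reference level.** With n = 15, the exact signed rank test rejects when the smaller rank sum is at most 25. The true two-sided level is 0.0479.

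**Step 3: why the plain mean drifts.** If the visits are exchangeable, r = week 48 / baseline has the same distribution as 1/r, so E[r] = E[(r + 1/r)/2] ≥ 1. Two nerves going 20 to 25 and 25 to 20 show it:

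- Mean of nerve changes: (25% − 20%)/2 = +2.5%.
- Relative change of the mean: (45 − 45)/45 = 0%.

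For independent error the drift is about CV². Averaging eight nerves of similar level first cuts it to about CV²/8.

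| CV | CV² | Simulated drift, mean of nerve changes | CV²/8 | Simulated drift, relative change of patient mean |
|---|---|---|---|---|
| 5% | 0.25% | 0.26% | 0.03% | 0.04% |
| 10% | 1.00% | 0.95% | 0.13% | 0.08% |
| 15% | 2.25% | 2.27% | 0.28% | 0.25% |
| 20% | 4.00% | 4.40% | 0.50% | 0.51% |

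**Step 4: rejection with no true mean change.** 3,000 trials per setting; ranges are over the three between-patient SDs. The simulation standard error near 5% is √(0.05 × 0.95/3000) = 0.004.

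| CV | Relative change of patient mean | Median of nerve changes | Mean of nerve changes |
|---|---|---|---|
| 5% | 0.045–0.053 | 0.045–0.052 | 0.046–0.066 |
| 10% | 0.048–0.061 | 0.049–0.055 | 0.067–0.095 |
| 15% | 0.047–0.051 | 0.044–0.051 | 0.106–0.164 |
| 20% | 0.043–0.053 | 0.040–0.055 | 0.162–0.258 |

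A second simulation (20,000 trials per cell, lognormal error) let errors correlate within a patient. At correlation 0.3 the plain mean rejects in 5.1%, 5.7% and 7.5% of trials at CV 5%, 10% and 15%.

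**Step 5: stacking.** Testing 120 nerves (15 × 8) as separate observations rejects in 12% to 41% of trials when patients differ in true change (SD 0.05 to 0.10). This is the reading least supported by SAP 6 and 3.3.

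**Step 6: direction.** SAP 10.1.1 says "An improve is defined as an increase for the motor nerve conduction velocity, and as a decrease for distal latency", and it treats F wave latency and potential length as it treats distal latency. Upward drift would flatter velocity only; on the other three criteria it looks like worsening.

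**The case for a change.** The strongest case for a change is this. The SAP spells out capsule counts by time of day yet leaves this step unstated. SAP 6 names the arithmetic mean first, and SAP 10.1.2 lists nerve-level relative changes, so averaging them is an easy step for a programmer. On timing, the SAP says: "This Statistical Analysis Plan was prepared and signed prior to the database lock after all patients had completed the study". The pilot is also meant to inform the size of a later trial, and the pooling affects the mean and SD carried forward. Finally, even two sound choices can split at 5%: with a true log change of 0.03 or 0.05, CV 10% or 15% and between-patient SD 0.05, the median and the relative change of the mean fell on opposite sides in 13% to 19% of trials.

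Part of this stands. The visible text does not name the statistic, and it does not strictly exclude a plain mean of nerve changes. Nerves must also be paired, because LOCF cannot fill a nerve missing at both week 24 and week 48. With assumed leg-only loss of 5% or 10% of nerves, CV 5% and correlation 0.3, an unpaired raw mean of latency rejects in 8.5% or 19.8% of trials. Restricted to paired nerves it rejects in 4.7% in both cases. No document suggests that loss pattern, and random loss gives 4.8% or 4.5%.

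The rest carries less weight. Two valid tests at moderate power often disagree near a cut-off, which does not make either one wrong. Signing before database lock is what Protocol 7.1.9 planned, and late signing bears equally on every choice in the SAP. Since every nerve's change is listed, any mean or SD needed for a later trial can be recomputed.

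**Conclusion.** No change to the plan is needed. The missing word is a detail that the surrounding text largely settles: pool each patient's nerves at each visit, apply the SAP 10.1.1 formula, and test at most 15 patient values. On that reading the null rejection rate was 0.043 to 0.061 against an attainable 0.0479. This rests on the assumed CVs of 5% to 20%, independent visit errors and matched nerves.

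The upward drift is real but belongs to a statistic the SAP does not ask for. Its size depends on inputs the documents do not give: negligible at CV 5% with correlation 0.3 (5.1%), material only when error is large and nearly independent across nerves.

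The consequence is small in any case. SAP 2.2 introduces these tests as a sensitivity analysis, Protocol 7.1.3 treats all endpoints as exploratory, and without a control arm a p-value against zero cannot be credited to the drug. The primary responder count uses individual nerves and is untouched. The separate shells may already name the statistic.
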